## PROTOCOL REVISION HISTORY

Protocol Version Number	Date
Version 1.0 (Original)	02 Sep 2021
Version 2.0	07 Oct 2021
Version 3.0	25 Feb 2022
Version 4.0	07 Dec 2022

Refer to [Appendix 6](#) for a cumulative listing of Protocol Summary of Changes and Rationale.

## STUDY SYNOPSIS

Protocol number: THE630-21-101	Study Treatment: THE-630
Study Title: A Phase 1/2 Study of the Safety, Pharmacokinetics and Anti-Tumor Activity of the Oral KIT Inhibitor THE-630 in Patients with Advanced Gastrointestinal Stromal Tumors (GIST)	
Site(s): Multi-site study. Approximately 7 sites in the United States will enroll for the Dose Escalation (Phase 1). An additional 18-20 sites will enroll for the Expansion (Phase 2) from within the United States and globally and may participate in backfill enrollment in the Phase 1 portion of the study.	
Study period (planned): Approximately 54 months	Clinical phase: Phase 1/2
Study Design: 
This is a first-in-human (FIH), multicenter, non-randomized, open-label Phase 1/2 study to evaluate the safety, pharmacokinetics (PK) and anti-tumor activity of oral THE-630 in patients with advanced GIST. The study will be conducted in two parts: a dose escalation phase, followed by an expansion phase.
 
Dose Escalation (Phase 1)
 
The patient population of the initial dose escalation phase (Phase 1) of the trial will include patients with unresectable or metastatic GIST. Patients must have disease progression on or be intolerant to imatinib therapy and have also received at least 1 of the following: sunitinib, regorafenib, ripretinib, or avapritinib. The objectives of the dose escalation phase are to determine the safety, PK profile, and recommended Phase 2 dose (RP2D) of orally administered THE-630 in these patients.
 
The dose escalation phase of this trial will employ sequential dose escalation of oral THE-630 using a standard 3+3 design, starting at 3 mg once daily (QD) and increasing in increments until the maximum tolerated dose (MTD) is identified. Initially, 3 patients will be enrolled at 3 mg administered orally QD and will be followed for 28 days. Increases of up to 100% over the previous dose level cohort will be employed until a <math>\geq</math> grade 2 non-hematologic adverse event (AE) where relationship to THE-630 cannot be ruled out, a <math>\geq</math> grade 3 hematologic AE where relationship to THE-630 cannot be ruled out is observed, a protocol defined dose limiting toxicity (DLT) is observed (either within the 28-day DLT period or an AE that otherwise would qualify as a DLT but occurs outside of that interval), or the dose level of 48 mg QD is reached. Further dose escalation will involve increments of no more than 50% of the previous dose, depending on safety findings, as long as there is no more than 1 of 6 patients in a cohort with a DLT. Alternative dosing regimens may be explored depending on initial PK findings and safety and tolerability data. Should a modification be required, the dose escalation scheme will be altered by interpolating non-once daily schedules into the initial escalation scheme. Prior to implementation of any alternative non-once daily dosing schedule, the protocol will be amended to describe the planned evaluation and justification for the specific alternative dosing schedule.
 
Each dose escalation cohort will have a minimum of 3 patients enrolled and followed for 28 days. Increasing to the next dose level will depend on the safety findings of the previous cohorts. Expansion of a cohort from 3 to 6 patients will occur if 1 of 3 patients experiences a DLT at a given dose. If 1 or more patients experience a DLT in the additional 3 patients in a dose cohort (i.e., for a total of <math>\geq 2</math> of 6 patients with a DLT), the dose level will be designated to have exceeded the MTD. If no patients experience a DLT in the additional 3 patients (i.e., for a total of <math>\leq 1</math> of 6 patients with a DLT), dose escalation will continue. In the case of non-safety-related dropouts during the first cycle of treatment, a cohort may be expanded to replace non-safety-related dropout patients.
 
Additional patients may be enrolled in one or more dose levels that have been shown to have not exceeded the MTD (up to 20 patients per dose level; up to 40 additional patients total), defined as backfill enrollment.
 
The specific dose for each subsequent cohort will be determined at a dose-escalation meeting that includes the Study Investigators and the Sponsor Clinical Study Team. Dose-escalation meetings will occur after all patients in the current cohort have completed at least 28 days of observation after their first dose of THE-630 or have experienced a DLT. Dose escalation will continue until the MTD or a RP2D below the MTD has been determined.
 
Intra-patient dose escalation will be allowed according to the following scheme. All patients in the dose escalation phase will have the option to increase dose beyond that which was initially assigned while on the study if the
	

following conditions are met: 1) the patient tolerated their starting dose without a DLT or dose reductions or interruptions because of an AE for which relationship to THE-630 cannot be ruled out, 2) the Cycle 3 PK sample has been drawn per protocol, and 3) the proposed next dose level has been evaluated and it has been shown that it does not exceed the MTD. There must be Investigator and Sponsor medical monitor approval in place before an intra-patient dose escalation can begin.

### **Expansion (Phase 2)**

Once a RP2D has been determined, the expansion phase (Phase 2) will enroll 3 cohorts of patients with unresectable or metastatic GIST defined by prior therapy:

- Cohort 1: Patients with unresectable or metastatic GIST who have progressed on or are intolerant to imatinib, sunitinib, regorafenib and ripretinib ( $\geq 5^{\text{th}}$  Line).
- Cohort 2: Patients with unresectable or metastatic GIST who have progressed on or are intolerant to imatinib, sunitinib and 0-1 additional lines of therapy in the advanced/metastatic setting (3rd-4th Line).
- Cohort 3: Patients with unresectable or metastatic GIST who have progressed on or are intolerant to imatinib (including in the adjuvant setting) and who have not received additional systemic therapy for advanced GIST (2nd Line).

The safety and tolerability of orally administered THE-630 will continue to be assessed in the expansion cohorts. However, the primary objective of the expansion component of the trial is to evaluate the anti-tumor activity of THE-630 in these GIST patient populations, as assessed by the Investigator, according to modified Response Evaluation Criteria in Solid Tumors (RECIST) version 1.1 (Demetri, 2013) (Appendix 1) for patients with GIST. Efficacy endpoints will include confirmed objective response rate (ORR), best overall response, best target lesion response, time to response, duration of response (DOR), disease control rate (DCR), Clinical Benefit Rate (CBR) at 16 weeks, progression-free survival (PFS) and overall survival (OS).

Exploratory biomarker evaluation of the mutation status of KIT, platelet-derived growth factor receptor alpha (PDGFRA) and other genes implicated in tumor biology, and/or drug metabolism may be determined through analyses of tumor tissue and blood plasma samples to evaluate biomarkers of THE-630 efficacy and safety. An optional biopsy will be taken at the time of disease progression on THE-630 for patients who consent to the procedure. Formalin-fixed, paraffin-embedded (FFPE) tumor tissue will be processed centrally and used for exploratory molecular genetic analysis.

### **Study Objectives:**

#### **Dose Escalation (Phase 1):**

**Primary:** To determine the safety profile of oral THE-630, including the DLTs, MTD, and RP2D

#### **Secondary:**

- To determine the PK profile of oral THE-630 and its active metabolite THE-973
- To document preliminary evidence of antitumor activity of oral THE-630 in patients with advanced GIST

#### **Expansion (Phase 2):**

**Primary:** To determine the antitumor activity of oral THE-630 in patients with advanced GIST

#### **Secondary:**

- To evaluate the safety profile of oral THE-630
- To further characterize the PK profile of oral THE-630 and its active metabolite THE-973

#### **Both Dose Escalation (Phase 1) and Expansion (Phase 2):**

**Exploratory:** To explore associations between tumor and plasma biomarkers and THE-630 efficacy and safety

**Study Endpoints:**

Dose Escalation (Phase 1):

**Primary:** Safety profile of oral THE-630, including identification of DLTs and MTD, and determination of the RP2D

**Secondary:**

- Plasma PK parameters of THE-630 and its active metabolite THE-973 after single oral dose and at steady state after multiple oral doses
- Efficacy assessments, according to modified RECIST 1.1 for patients with GIST including: confirmed ORR, best overall response, best target lesion response, time to response, DOR, DCR, CBR at 16 weeks, PFS, and OS

Expansion (Phase 2):

**Primary:** Confirmed ORR, according to modified RECIST 1.1 for patients with GIST

**Secondary:**

- Efficacy assessments, according to modified RECIST 1.1 for patients with GIST, including: DOR, best overall response, best target lesion response, time to response, DCR, CBR at 16 weeks, PFS, and OS
- Safety profile of oral THE-630
- Plasma PK parameters of THE-630 and its active metabolite THE-973, after a single oral dose and at steady state after multiple oral doses

Both Dose Escalation (Phase 1) and Expansion (Phase 2):

**Exploratory:** Molecular analysis of patients' tumor and plasma may include, but is not limited to:

- a. Presence of KIT mutations
- b. Presence of PDGFRA mutations

**Inclusion Criteria:**

Patients must meet the following criteria to be eligible for participation in the study:

1. Male or female patient  $\geq$  18 years of age.
2. For Dose Escalation Phase Cohorts (Phase 1):
  - a. Have histologically- or cytologically-confirmed unresectable or metastatic GIST.
  - b. Have progressed on or are intolerant to imatinib therapy and have also received at least 1 of the following: sunitinib, regorafenib, ripretinib, or avapritinib.
3. For Expansion Phase Cohorts (Phase 2):
  - a. Cohort 1:
    - i. Have histologically- or cytologically confirmed unresectable or metastatic GIST.
    - ii. Have progressed on or are intolerant to imatinib, sunitinib, regorafenib and ripretinib.
  - b. Cohort 2:
    - i. Have histologically- or cytologically confirmed unresectable or metastatic GIST.
    - ii. Have progressed on or are intolerant to imatinib and sunitinib. Patients in this cohort are allowed to have received up to 1 additional line of therapy in the advanced/metastatic setting.

- c. Cohort 3:
  - i. Have histologically- or cytologically confirmed unresectable or metastatic GIST.
  - ii. Have progressed on or are intolerant to imatinib (including in the adjuvant setting).
  - iii. Have not received additional systemic therapy for advanced GIST.
4. Have at least 1 measurable lesion as defined by modified RECIST 1.1 ([Appendix 1](#)).
5. Have archival or new tumor biopsy tissue available to submit for mutational testing. A tumor sample obtained after most recent prior systemic anticancer therapy is preferred. Patients without appropriate archival tissue available may be discussed with the study medical monitor and approved for enrollment on a case-by-case basis.
6. Have Eastern Cooperative Oncology Group (ECOG) performance status (PS) of 0-2 ([Appendix 2](#)).
7. Adequate renal and hepatic function as defined by the following criteria:
  - a. Total serum bilirubin  $\leq 1.5 \times$  upper limit of normal (ULN) ( $< 3.0 \times$  ULN for patients with Gilbert syndrome),
  - b. Alanine aminotransferase (ALT) and aspartate aminotransferase (AST)  $\leq 3 \times$  ULN (or  $\leq 5 \times$  ULN if liver function abnormalities are due to underlying malignancy), and
  - c. Estimated (using Cockcroft-Gault formula or using the method standard for the institution) or measured creatinine clearance  $\geq 60$  mL/min.
8. Adequate bone marrow function as defined by the following criteria:
  - a. Absolute neutrophil count (ANC)  $\geq 1.5 \times 10^9/L$ ,
  - b. Platelet count  $\geq 75 \times 10^9/L$ , and
  - c. Hemoglobin  $\geq 9.0$  g/dL.
9. For female patients of childbearing potential, have a negative serum or urine beta human chorionic gonadotropin ( $\beta$ -hCG) pregnancy test within 7 days prior to the first dose of study drug.
  - a. Note: female patients of nonchildbearing potential (postmenopausal; hysterectomy; bilateral salpingectomy; or bilateral oophorectomy) do not require a pregnancy test.
10. Female patients of childbearing potential must agree to abstain from heterosexual intercourse or use a highly effective form of contraception with their sexual partners during the dosing period and for a period of at least 30 days after the end of treatment. Male patients with partners of childbearing potential must agree that they will abstain from heterosexual intercourse or use condoms and their partners will use highly effective contraceptive methods during the dosing period until at least 90 days after the last dose of study drug.
11. All toxicities from prior therapy have resolved to  $\leq$  grade 1 according to the National Cancer Institute Common Terminology Criteria for Adverse Events (NCI CTCAE v5.0) ([Appendix 3](#)), or have resolved to baseline, at the time of first dose of study drug. Note: treatment-related grade  $> 1$  alopecia, treatment-related grade 2 peripheral neuropathy, and treatment-related grade 2 hypothyroidism on a stable dose of thyroid hormone replacement therapy are allowed if deemed irreversible.
12. Patient or legal guardian, if permitted by local regulatory authorities, signed and dated informed consent indicating that the patient has been informed of all pertinent aspects of the study.
13. Willingness and ability to comply with scheduled visits and study procedures.

**Exclusion Criteria:**

Patients meeting any of the following criteria will not be eligible for participation in the study:

1. Received systemic anticancer therapy (including cytotoxic chemotherapy, investigational agent, antineoplastic monoclonal antibodies, or immunotherapy) less than 5 half-lives or 14 days (whichever is shorter) prior to the first dose of study drug.
2. Patients known to be both KIT and PDGFRA wild-type.
3. Received radiotherapy within 14 days prior to the first dose of study drug.
4. Major surgical procedure within 28 days of the first dose of study drug. Minor surgical procedures such as central venous catheter placement or minimally invasive biopsy are allowed.
5. Have known untreated or active central nervous system metastases.
6. 12-lead electrocardiogram (ECG) demonstrating QT interval corrected by Fridericia's formula (QTcF) > 470 msec at screening, or history of long QTc syndrome.
7. Have significant, uncontrolled, or active cardiovascular disease, including, but not restricted to:
  - a. Myocardial infarction (MI) within 6 months prior to the first dose of study drug
  - b. Unstable angina within 6 months prior to first dose of study drug
  - c. Symptomatic congestive heart failure (New York Heart Association classes II-IV) ([Appendix 4](#)) within 6 months prior to first dose of study drug
  - d. Clinically significant, uncontrolled atrial arrhythmia (as determined by the Investigator)
  - e. Any history of ventricular arrhythmia
  - f. Cerebrovascular accident or transient ischemic attack within 6 months prior to first dose of study drug
  - g. Uncontrolled hypertension at study entry. Patients with hypertension should be under treatment on study entry to control blood pressure.
8. Have an active uncontrolled infection, including, but not limited to, the requirement for intravenous antibiotics.
9. Patients with a known allergy or hypersensitivity to any component of the study drug. Patients with a history of Stevens-Johnson syndrome on a prior tyrosine kinase inhibitor (TKI) are excluded.
10. Any active bleeding excluding hemorrhoidal or gum bleeding.
11. For patients with a known human immunodeficiency virus (HIV) infection, have CD4+ T-cell counts <350 cells/uL or history of acquired immunodeficiency syndrome (AIDS)-defining opportunistic infection within the past 12 months. Patients with HIV infection should be on established antiretroviral therapy (ART) for at least 4 weeks and have an HIV viral load less than 400 copies/mL prior to enrollment.
12. Has known active hepatitis B virus (HBV) or hepatitis C virus (HCV) infection, as evidenced by detectable viral load (HBV-DNA or HCV-RNA, respectively). Risk of HBV reactivation should be considered in all patients and the need for anti-HBV prophylaxis should be carefully assessed. Patients with chronic HBV infection with history of active disease who meet the criteria for anti HBV therapy should be on a suppressive antiviral therapy to be eligible for enrollment. Patients who are HCV Ab positive but HCV RNA negative due to prior treatment or natural resolution are eligible. Patients on concurrent HCV treatment at the time of enrollment are allowed if HCV RNA negative.
13. Pregnant or breastfeeding.
14. Malabsorption syndrome or other illness that could affect oral absorption.
15. Patients with prior or concurrent malignancies other than GIST are allowed, except in the case where, in the opinion of the Investigator, the natural history or treatment of the other malignancy has the potential to interfere with the safety or efficacy assessment of the study drug.
16. Have any condition or illness that, in the opinion of the Investigator, might compromise patient safety or interfere with the evaluation of the safety of the drug.

**Number of patients (total and for each cohort):**

Approximately 90-160 patients will be enrolled in the study, assuming the following:

- Dose Escalation (Phase 1): Approximately 30-100 patients, across an estimated 5 to 10 dose levels, which may include expanded cohorts to better inform selection of the RP2D (i.e., backfill enrollment)
- Expansion Cohorts (Phase 2)
  - Cohort 1: approximately 20 patients
  - Cohort 2: approximately 20 patients
  - Cohort 3: approximately 20 patients

**Approximate minimum duration of patient participation:**

3 months across the following study periods:

- Screening period: 2-3 weeks
- Treatment period: at least 1 cycle (28 days)
- Follow-up period after last dose of study drug: 30 days

Thereafter, patients are to be followed for subsequent antineoplastic therapy and survival approximately every 3 months until death, withdrawal of consent or closure of the study by the Sponsor.

**Study Drug Dosage:**

THE-630 drug product will be initially supplied as 1 mg, 3 mg, 12 mg, and 20 mg hard gelatin capsules containing a formulated blend of excipients and THE-630 HCl. Higher strengths of capsules and/or formulated tablets will be introduced depending on the safety, PK, and biological activity of THE-630.

The dose escalation phase of the proposed phase 1/2 trial will employ sequential, dose escalation of oral THE-630 using a standard 3+3 design, starting at a dose of 3 mg administered orally QD, and increasing in increments until the MTD is identified. Alternative dosing regimens may be explored depending on PK findings and safety and tolerability data. Should a modification be required, the dose escalation scheme will be altered by interpolating non-once daily schedules into the initial escalation scheme. Alternative dosing regimens will be in standalone cohorts and will follow the same Schedule of Events ([Table 1](#)) as outlined herein. Intermediate doses between the MTD and the next lower dose may be explored.

**Study Drug Administration:**

THE-630 will be administered orally QD with a glass of water (at least 8 ounces or 250 mL) in a fasted state, with no food intake from 2 hours before until 1 hour after study drug administration.

Each dose should be administered at approximately the same time each day. Patients should be instructed to swallow capsules whole and to not chew the capsules. THE-630 capsules should not be opened or dissolved into liquid or food. If a patient vomits after taking a dose, the patient should not take an extra dose. Patients who forget to take or miss a dose (i.e., >6 hours after schedule time of administration) should not make up the missed dose.

Patients will continue with the study treatment until progression of disease as determined by the Investigator, unacceptable toxicity, death or consent withdrawal.

**Concomitant Treatment and Additional Precautions:**

Palliative therapy and supportive care are permitted during the course of the trial for management of symptoms and underlying medical conditions that may develop during the study. The inclusion and exclusion criteria should be used to determine which medications a patient is allowed to be on at the time of screening and study entry. Once a patient has begun treatment, a condition may arise that requires the initiation of a new concomitant treatment.

After a patient has begun study treatment, the addition of the following concurrent treatments are prohibited:

1. Any other systemic anticancer therapy including, but not limited to, chemotherapeutic agents, immunotherapy, biological response modifiers (excluding growth factors), and/or systemic hormonal

therapy. Note: local radiotherapy used for palliative or symptomatic control of disease is allowed with appropriate treatment interruption at the discretion of the Investigator

2. Medications that are potent inhibitors of [REDACTED], as THE-630 is observed to be a [REDACTED] substrate in vitro (refer to [Appendix 5](#) for a list of these medications)
3. Extensive surgery requiring in-patient care (patients may have an interruption in therapy for up to 4 weeks should emergency surgery be required)
4. Use of any other investigational drug or device.

*In vitro*, THE-630 is an inhibitor of [REDACTED]. Therefore, THE-630 may have the potential to increase plasma concentrations of co-administered substrates of [REDACTED]. Medications that are [REDACTED] substrates with a narrow therapeutic index should be used with caution (refer to [Appendix 5](#) for a list of these medications).

The effect of THE-630 in wound healing is not known; therefore, caution is advised on the grounds of potential antiangiogenic effect for any surgical procedures during the study. The appropriate interval of time between surgery and THE-630 required to minimize the risk of impaired wound healing and bleeding has not been determined. In the event unexpected major surgery is necessary during study participation, THE-630 dosing should be stopped 1 week prior to surgery. After major surgery, THE-630 should not be administered for at least 2 weeks and until clinical assessment of satisfactory wound healing.

The light absorption characteristics of THE-630 suggest the possibility that THE-630 treatment will be associated with phototoxicity. Patients should be advised to apply sunscreen and wear appropriate clothing to avoid direct sun exposure. Patients should also be advised to avoid high intensity ultraviolet B (UVB) sources such as tanning beds, tanning booths and sunlamps.

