## 4.2 Exclusion Criteria

Patients meeting any of the following criteria will not be eligible for participation in the study:

1. Received systemic anticancer therapy (including cytotoxic chemotherapy, investigational agent, antineoplastic monoclonal antibodies, or immunotherapy) less than 5 half-lives or 14 days (whichever is shorter) prior to the first dose of study drug.
2. Patients known to be both KIT and PDGFRA wild-type.
3. Received radiotherapy within 14 days prior to the first dose of study drug.
4. Major surgical procedure within 28 days of the first dose of study drug. Minor surgical procedures such as central venous catheter placement or minimally invasive biopsy are allowed.
5. Have known untreated or active central nervous system metastases.
6. 12-lead electrocardiogram (ECG) demonstrating QT interval corrected (QTc) by Fridericia's formula  $> 470$  msec at screening, or history of long QTc syndrome.
7. Have significant, uncontrolled, or active cardiovascular disease, including, but not restricted to:
  - a. Myocardial infarction (MI) within 6 months prior to the first dose of study drug
  - b. Unstable angina within 6 months prior to first dose of study drug
  - c. Symptomatic congestive heart failure (New York Heart Association classes II-IV) ([Appendix 4](#)) within 6 months prior to first dose of study drug
  - d. Clinically significant, uncontrolled atrial arrhythmia (as determined by the Investigator)
  - e. Any history of ventricular arrhythmia
  - f. Cerebrovascular accident or transient ischemic attack within 6 months prior to first dose of study drug
  - g. Uncontrolled hypertension at study entry. Patients with hypertension should be under treatment on study entry to control blood pressure.
8. Have an active uncontrolled infection, including, but not limited to, the requirement for intravenous antibiotics.
9. Patients with a known allergy or hypersensitivity to any component of study drug. Patients with a history of Stevens-Johnson syndrome on a prior TKI are excluded.
10. Any active bleeding excluding hemorrhoidal or gum bleeding.

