11. For patients with a known human immunodeficiency virus (HIV) infection, have CD4+ T-cell counts  $< 350$  cells/uL or history of acquired immunodeficiency syndrome (AIDS)-defining opportunistic infection within the past 12 months. Patients with HIV infection should be on established antiretroviral therapy (ART) for at least 4 weeks and have an HIV viral load less than 400 copies/mL prior to enrollment.

12. Has known active hepatitis B virus (HBV) or hepatitis C virus (HCV) infection, as evidenced by detectable viral load (HBV-DNA or HCV-RNA, respectively). Risk of HBV reactivation should be considered in all patients and the need for anti-HBV prophylaxis should be carefully assessed. Patients with chronic HBV infection with history of active disease who meet the criteria for anti HBV therapy should be on a suppressive antiviral therapy to be eligible for enrollment. Patients who are HCV Ab positive but HCV RNA negative due to prior treatment or natural resolution are eligible. Patients on concurrent HCV treatment at the time of enrollment are allowed if HCV RNA negative.
13. Pregnant or breastfeeding.
14. Malabsorption syndrome or other illness that could affect oral absorption.
15. Patients with prior or concurrent malignancies other than GIST are allowed, except in the case where, in the opinion of the Investigator, the natural history or treatment of the other malignancy has the potential to interfere with the safety or efficacy assessment of the study drug.
16. Have any condition or illness that, in the opinion of the Investigator, might compromise patient safety or interfere with the evaluation of the safety of the drug.

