## 5.7 Prior and Concomitant Therapy

### 5.7.1 Prior Therapy and Procedures

History of prior cancer therapy will be recorded at screening, and concomitant cancer therapy will be recorded during the study on the appropriate eCRF for each patient. Reasonable efforts will be made to collect information on all prior cancer therapy received by the patient (e.g., surgeries, chemotherapy, radiotherapy, immunotherapy, biologics). The information must be obtained from the patient's medical chart and recorded on the appropriate eCRF.

Table 6 details prior therapies that require a minimum washout period. The washout period is relative to the first dose of study drug.

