**Table 6 Excluded Prior Therapy and Washout Periods**

Treatment	Washout Period
Systemic anticancer therapy (i.e., cytotoxic chemotherapy, investigational agent, antineoplastic monoclonal antibodies, immunotherapy)	14 days or 5 half-lives (whichever is shorter)
Radiotherapy	14 days
Medications that are potent inhibitors of [REDACTED], as THE-630 is observed to be a substrate of [REDACTED] in vitro (refer to Appendix 5 for a list of these medications).	7 days
Major surgical procedures (minor surgical procedures such as central venous catheter placement or minimally invasive biopsy are allowed)	28 days

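### The synopsis leaves entry medications to eligibility criteria that never mention potent inhibitors, while Section 5.7 requires a 7-day washout and bars them on treatment

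*Protocol*

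**What the plan says.** **Synopsis, Concomitant Treatment and Additional Precautions.** The "inclusion and exclusion criteria should be used to determine which medications a patient is allowed to be on at the time of screening" and at study entry. For the period after dosing starts: "After a patient has begun study treatment, the addition of the following concurrent treatments are prohibited". Item 2 of the list that follows is potent inhibitors of a pathway whose name is redacted. It refers to Appendix 5 and gives as its reason that THE-630 is a substrate in vitro.

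**Sections 4.1 and 4.2, repeated in the synopsis.** There are 13 inclusion and 16 exclusion criteria. Section 4.2 opens with "Patients meeting any of the following criteria will not be eligible for participation in the study".

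**Section 5.7.1 and Table 6.** Four kinds of prior therapy need a minimum washout, and "The washout period is relative to the first dose of study drug". The row at issue begins "Medications that are potent inhibitors of [REDACTED], as THE-630 is observed to be a substrate of [REDACTED"; its washout is 7 days.

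**Section 5.7.2 and Table 7.** Potent inhibitors are excluded as concomitant treatment during the treatment period, with no limit to drugs newly started.

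**SAP 4.1.2 and 4.1.3.** The Enrolled Set is limited to screened patients who satisfy the eligibility criteria. The Full Analysis Set (FAS) is the enrolled patients who took at least one dose, and SAP 4.15 runs the safety analyses on the FAS.

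**The concern.** The washout is an entry safeguard in a first-in-human study, but the entry steps work from a list that leaves it out. Section 6.2 calls for a review of the criteria at screening and defines a screen failure by them. Section 6.3.1 reconfirms them on Cycle 1 Day 1, and Section 10.6 makes the investigator responsible for enrolling only patients who meet them. A site that follows the synopsis and the numbered criteria could conclude that a patient already taking a potent inhibitor is eligible, is not a screen failure and, by simply continuing the drug, is not adding anything. Tables 6 and 7 forbid both the entry and the continuation.

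Such a breach would also be hard to see in the planned output. SAP Table 14.1.1.3 counts inclusion and exclusion violations, and a missed washout that is not a criterion is not one of those. SAP 4.9 neither summarizes nor lists prior and concomitant medications. The breach would reach a planned table only if it were classed as a major deviation under SAP 4.5.

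A second problem appears when the analysis sets are read alongside the criteria. If the Enrolled Set requires eligibility and the FAS is drawn from it, any dosed patient who breached any criterion falls out of the safety tables.

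**Working it through.** No sample size, error rate or estimate is involved, and the plan states no figure to reproduce. The check compares texts and counts.

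**Step 1. Match each Table 6 washout to a numbered exclusion in Section 4.2.**

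| Table 6 row | Washout | Matching exclusion |
|---|---|---|
| Systemic anticancer therapy | 14 days or 5 half-lives, whichever is shorter | 1 |
| Radiotherapy | 14 days | 3 |
| Potent inhibitors (Appendix 5) | 7 days | none |
| Major surgery | 28 days | 4 |

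Rows 4, matched 3, unmatched 4 − 3 = 1. The sponsor's own pattern is that a washout is also an exclusion, and this row breaks it.

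**Step 2. Search every criterion.** 13 + 16 = 29 criteria per list. Those naming potent inhibitors, Appendix 5 or Table 6: 0 of 29 in the synopsis and 0 of 29 in Sections 4.1 and 4.2. The nearest candidates do not cover them. Exclusion 1 concerns anticancer therapy, exclusion 14 absorption, and exclusion 16 a condition or illness rather than a medication.

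**Step 3. Rule out redaction.** In the passages compared, only the pathway name is blacked out. The criteria run 1 to 13 and 1 to 16 without a gap and carry no redaction on this point.

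**Step 4. Compare the rules for a patient taking a potent inhibitor at screening.**

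| Question | Synopsis and criteria, read literally | Section 5.7 |
|---|---|---|
| May the patient start within 7 days of the last inhibitor dose? | Yes; no criterion is breached | No (Table 6) |
| May the patient continue the inhibitor on treatment? | Not an addition, so not caught | No (Table 7) |

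Section 5.7.2 repeats much of the synopsis paragraph but contains neither the sentence deferring to the criteria nor the restriction to additions. The mismatch is therefore between the synopsis with its eligibility list and Section 5.7. Section 5.7 is consistent within itself.

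**Step 5. Trace the analysis sets for a dosed patient who breached a criterion.** Not eligible, so not in the Enrolled Set (SAP 4.1.2); so not in the FAS (SAP 4.1.3); so not in the safety tables (SAP 4.15). Protocol Section 9.2 defines the FAS by enrollment and dosing without an eligibility test, and Section 9.6 makes every dosed patient evaluable for safety. The SAP's literal result conflicts with both. This holds for all the existing criteria and does not depend on adding one.

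**The case against.** The strongest reply is that the rule exists and binds. Section 10.5 requires the protocol to be followed as written, and Section 10.6 opens with adherence to the whole document. Table 6 is titled as a list of excluded prior therapy. Medications are recorded at screening and on Cycle 1 Day 1, synopsis item 2 names the inhibitors, and Appendix 5 sends queries to the medical monitor. The synopsis also does not say that the criteria are the only test. The restriction to additions is strained as well: items 1 and 4 of the same list are other anticancer therapy and other investigational products, and nobody would let a patient continue those because they were started earlier. All of this stands. It makes the point minor, but it does not supply the missing criterion or reconcile the synopsis sentence with Table 6.

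Four stronger readings are tempting and are not supported:

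- **The protocol lacks the safeguard.** It does not; Section 5.7 states it clearly.
- **Patients on long-term drugs are the ones at risk.** Exclusions 7g, 11 and 12 expect some patients to be on antihypertensive or antiviral treatment at entry. The drug list in Appendix 5 and the pathway are not shown, so nothing can be inferred about whether any of those drugs is a listed inhibitor.
- **Exposure, dose-limiting toxicities or escalation decisions were distorted.** The basis is an in vitro finding on a redacted pathway, with no count of patients, so no size can be given and it may be nil. Nor is there a case for an inhibitor marker in the DLT listing: SAP 4.9 drops medication data, and Appendix 5 says its list is not exhaustive and calls for medical judgement.
- **The FAS wording matters because a new exclusion would remove patients.** Enrollment is closed, so a criterion added now cannot reclassify anyone. The FAS correction rests on the existing criteria alone.

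**Conclusion.** The point holds as a **minor** inconsistency between the synopsis with its eligibility list and Section 5.7. One of four washouts has no matching criterion, and none of the 29 criteria in either list names the drugs. The consequence is an avoidable entry error at a site that screens from the criteria alone. How many patients entered this way is not in the documents and may be zero. According to SAP 1, enrollment stopped at 32 in Phase 1 and Phase 2 will not start, so correcting the protocol wording protects no further patient in this trial and matters only if the text is used again.

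The FAS wording is a separate and real error of definition that bears on the remaining analysis. Its practical effect depends on whether any dosed patient breached a criterion, which the documents do not report and which may also be none. Both conclusions assume only that the texts are read as written.

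**What to change.** 1. **Protocol Section 4.2 and synopsis.** Add a numbered exclusion for any potent inhibitor covered by Appendix 5 taken within 7 days before the first dose of THE-630.
2. **Synopsis, concomitant treatment.** Replace *the addition of* with *the use of*, so that it agrees with Table 7.
3. **SAP 4.1.2 and 4.1.3, whether or not the first two are adopted.** Define the FAS as every patient who received at least one dose of THE-630, whatever criterion was breached. This restores agreement with Protocol Sections 9.2 and 9.6.

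The cost is one line in two places, one changed phrase and one SAP sentence. The only downside of the exclusion is that, in any further use of the protocol, a few candidates would wait up to 7 days or not enroll, which Table 6 already intends.
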